### 6.13.1. Extent of Exposure

Mean and median modal dose and total patient days of exposure will be reported for all the treatment arms. Descriptive statistics will be provided for subject days of exposure and the frequency of subjects falling into the following different exposure ranges will also be summarized:

- $\geq 4$  days,  $\geq 7$  days, and  $\geq 10$  days, and  $\geq 14$  days
- $> 0$  to  $< 4$  days,  $\geq 4$  days to  $< 7$  days,  $\geq 7$  days to  $< 10$  days,  $\geq 10$  days to  $< 14$  days and  $\geq 14$  days.

In addition, study duration will be analyzed in a similar fashion to what was planned for exposure duration but expanding ranges to 28 days.

### 6.13.2. Adverse Events

The planned summaries for AEs are provided in [Table KHAA.6.9](#) and are described more fully in compound level safety standards and in the AE-related PhUSE white paper (Analysis and Displays Associated with Adverse Events: Focus on Adverse Events in Phase 2-4 Clinical Trials and Integrated Summary Documents [PhUSE 2017]).

**Table KHAA.6.9. Summary Tables Related to Adverse Events**

Analysis	Population or Analysis Set
An overview table, with the number and percentage of subjects who experienced a TEAE, serious adverse event, death, discontinued from study treatment due to an adverse event	Safety population
An overview table, with the number and percentage of subjects who experienced an event, serious adverse event, death, discontinued from study due to an adverse event	Follow-up analysis set
The number and percentage of subjects with TEAEs using MedDRA Preferred Term nested within System Organ Class	
The number and percentage of subjects with FEAEs using MedDRA Preferred Term nested within System Organ Class	Follow-up analysis set
The number and percentage of subjects with TEAEs using MedDRA Preferred Term	Safety population
The number and percentage of subjects with TEAEs by maximum severity using MedDRA Preferred Term	Safety population
The number and percentage of subjects with TEAEs using MedDRA Preferred Term for the common TEAEs (occurred in $\geq 2\%$ before rounding of treated subjects)	Safety population
The number and percentage of subjects who experienced a serious adverse event (including deaths and SAEs temporally associated or preceding deaths) using MedDRA Preferred Term nested within System Organ Class	Safety population
The number and percentage of subjects who experienced a serious adverse event (including deaths and SAEs temporally associated or preceding deaths) using MedDRA Preferred Term nested within System Organ Class	Follow-up analysis set
Listing of All SAEs	Safety population
The number and percentage of subjects who permanently discontinued from study treatment due to an adverse event (including adverse events that led to death) using MedDRA Preferred Term nested within System Organ Class	Safety population
Listing of AEs which led to permanent discontinuation from the study treatment and from the study	Safety population

Abbreviations: AEs = adverse events; ITT = Intent-to-Treat; MedDRA = Medical Dictionary for Regulatory Activities; SAE = serious adverse event; TEAE = treatment-emergent adverse event.

### 6.13.3. Clinical Laboratory Evaluation

The planned summaries for clinical laboratory evaluations are provided in [Table KHAA.6.10](#) and are described more fully in compound level safety standards and in the laboratory-related PhUSE white papers (Analyses and Displays Associated with Measures of Central Tendency – Focus on Vital Sign, Electrocardiogram, and Laboratory Analyte Measurements in Phase 2-4 Clinical Trials and Integrated Submission Documents [PhUSE 2013] and Analyses and Displays Associated with Outliers or Shifts from Normal to Abnormal: Focus on Vital Signs, Electrocardiogram, and Laboratory Analyte Measurements in Phase 2-4 Clinical Trials and Integrated Summary Documents [PhUSE 2015]).

**Table KHAA.6.10. Summary Tables Related to Clinical Laboratory Evaluations**

Analysis	Population or Analysis Set
Box plots for observed and/or change from baseline values	Safety population
Common Terminology Criteria for Adverse Events (CTCAEs) shifts tables for labs	Safety population
Tables with the number and percentage of subjects who shift from normal/high to low (that is, treatment-emergent low) and the number and percentage of subjects who shift from normal/low to high (that is, treatment-emergent high) may be analyzed using appropriate and validated reference ranges	Safety population
Listing of abnormal findings for laboratory analyte measurements, including qualitative measures	Safety population

#### **6.13.4. Vital Signs and Other Physical Findings**

The planned summaries for vital signs (systolic blood pressure [BP], diastolic BP, pulse, weight, BMI, temperature) are provided in [Table KHAA.6.11](#) and are described more fully in compound level safety standards and in the vitals-related PhUSE white papers (Analyses and Displays Associated with Measures of Central Tendency – Focus on Vital Sign, Electrocardiogram, and Laboratory Analyte Measurements in Phase 2-4 Clinical Trials and Integrated Submission Documents [PhUSE 2013] and Analyses and Displays Associated with Outliers or Shifts from Normal to Abnormal: Focus on Vital Signs, Electrocardiogram, and Laboratory Analyte Measurements in Phase 2-4 Clinical Trials and Integrated Summary Documents [PhUSE 2015]).

**Table KHAA.6.11. Summary Tables Related to Vital Signs**

Analysis	Population or Analysis Set
Box plots for observed and/or change from baseline values	Safety population
Tables with the number and percentage of subjects who shift from normal/high to low (that is, treatment-emergent low) and the number and percentage of subjects who shift from normal/low to high (that is, treatment-emergent high); the limits are defined in the compound level safety standards and are based on literature.	Safety population

#### **6.13.5. Special Safety Topics**

This section includes safety topics of interest, whether due to observed safety findings, potential findings based on drug class, or safety topics anticipated to be requested by a regulatory agency for any reason. In general, safety topics of interest will be identified by 1 or more SMQs, by an Eli Lilly and Company- (Lilly-) defined MedDRA PT listing based upon the review of the most current MedDRA version, or by treatment-emergent relevant laboratory changes. The topics of interest may include, but may not be limited to:

- abnormal hepatic tests
- hematologic changes
- renal function effects
- elevations in creatinine phosphokinase

- serious infections, herpes zoster, and opportunistic infection,
- major adverse cardiovascular events and other cardiovascular events, and
- venous thromboembolic and arterial thromboembolic events.

Refer to the compound level safety standards for details of analyses of the special safety topics.

## 6.14. Subgroup Analyses

For primary and gated secondary endpoints, following subgroup analysis will be conducted:

- baseline disease severity:
  - hospitalized not requiring supplemental oxygen, requiring ongoing medical care (OS 4)
  - hospitalized requiring supplemental oxygen by prongs or mask (OS 5)
  - hospitalized requiring noninvasive ventilation or high-flow oxygen (OS 6)
  - OS 5 and OS 6 combined
- baseline steroid use: dexamethasone and/or other systemic corticosteroid used at baseline for primary study condition (Yes/No)
- baseline remdesivir use (Yes/No)

The following subgroups categorized into disease-related characteristics and demographic characteristics will be evaluated for primary endpoint. These analyses may also be conducted selectively on key secondary endpoints if applicable:

- patient demographic and characteristics subgroups:
  - gender (male, female)
  - age group (<65, ≥65)
  - baseline weight (<60 kg, ≥60 to <100 kg, ≥100 kg)
  - baseline BMI (<25 kg/m^2, ≥25 to <30 kg/m^2, ≥30 kg/m^2)
  - race (American Indian or Alaska Native, Asian, Black or African American, Native Hawaiian or Other Pacific Islander, White, Multiple)
  - baseline renal function status: impaired (eGFR <60 mL/min/1.73 m^2) or not impaired (eGFR ≥60 mL/min/1.73 m^2)
- geographic region subgroups:
  - region (US, Europe, Rest of World)
- baseline disease-related characteristics subgroups:
  - baseline disease duration of symptoms prior to enrollment:<7 days, ≥7 days

- preexisting comorbid conditions of interest: none, any

For subgroup analyses of categorical endpoints, a logistic regression model or proportional odds model using the Firth correction (Firth 1993) will be used to obtain a p-value for the treatment-by-subgroup interaction. The response variable will be each corresponding endpoint. The explanatory variables will be treatment, subgroup, treatment-by-subgroup interaction, and the baseline stratification variables (Section 6.1.4). Within each subgroup category, odds ratios (bariatric 4-mg over placebo) and associated CIs and p-values will be provided. Point estimates and CIs of the proportions and difference in proportions will be presented. For LOCF analyses the CIs will be based on the Newcombe-Wilson method without continuity correction. For multiple imputation analyses, proportions/percentages will be based on percentages in the multiply-imputed datasets; CIs will be based on the Wald method without continuity correction.

For ANOVA analyses of continuous endpoints, the following explanatory variables will be included for the test of interaction: treatment, subgroup, treatment-by-subgroup interaction and the baseline stratification factors (Section 6.1.4). The F test will be used to obtain a p value for treatment-by-subgroup interaction, type III sums of squares. Within each subgroup category, LS mean and associated p-values from ANOVA (using models given in Section 6.2.2) will be provided.

For the time-to-event endpoints, an unstratified log-rank test will be performed within each level of specified subgroups if sample sizes allow. Analysis of individual levels of subgroups will follow what is specified in Section 6.2.3, possibly with the use of the Firth correction.

Descriptive statistics will be provided for each treatment and stratum of a subgroup, regardless of sample size. Inferential statistics will be provided if sample sizes and event numbers are sufficiently large (e.g., >100 patients total and at least 1 event in each arm).

Additional subgroup analyses on efficacy may be performed as deemed appropriate and necessary.

Subgroup analyses for safety parameters will be specified in the List of Analyses for this study.

[Table KHAA.6.12](#) lists the analysis methods for the different subgroup analysis.

Table KHAA.6.12. Description of Subgroup Analyses for Primary and Key Secondary Endpoints

Measure	Variable	Subgroup	Analysis Method	Time Point
NIAID-OS	Proportion of patients who died or progressed to non-invasive ventilation or high-flow oxygen (OS $\geq$ 6)	ITT: Population 1 – baseline disease severity	Logistic regression using MI	By Day 28
		ITT: Population 2 – baseline disease severity	Logistic regression using MI	By Day 28
		ITT: Population 1 – baseline disease severity	Logistic regression using LOCF	By Day 28
		ITT: Population 2 – baseline disease severity	Logistic regression using LOCF	By Day 28
		All subgroups other than baseline disease severity	Logistic regression using LOCF	By Day 28
	Ventilator-free days (VFD)	All subgroups	ANOVA using LOCF	By Day 28
	Proportion of patients with 1-point improvement	All subgroups	Logistic regression using LOCF	Day 4, 7, 10, 14
	Time to recovery	All subgroups	Log-rank test using IETI	By Day 28
	Overall improvement	All subgroups	Proportional odds model using LOCF	Day 4, 7, 10, 14
	Duration of hospitalization	All subgroups	ANOVA using LOCF	By Day 28
All-cause mortality	All subgroups	Log-rank test	By Day 28	
Oxygen Saturation	Proportion of patients with change in oxygen saturation from <94% at baseline to $\geq$ 94% at the observed time point	All subgroups	Logistic regression using LOCF	Day 4, 7, 10, 14

Abbreviations: ANOVA = analysis of variance; IETI = infinite event time imputation; ITT = Intent-to-Treat; MI = multiple imputation; LOCF = last observation carried forward; NIAID-OS = National Institute of Allergy and Infectious Diseases ordinal scale; VFD = ventilator-free days.

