Subgroup analyses for the primary and selected key secondary outcomes will evaluate the treatment effect across the following subgroups: baseline OS (OS 4 vs. OS 5 and OS 6 combined), baseline usage of remdesivir (Y/N), baseline usage of corticosteroids (Y/N), geographic region, duration of symptoms prior to enrollment, age, sex, dexamethasone and/or other systemic corticosteroid used at baseline for primary study condition, and comorbidities (if

applicable). Interaction tests will be conducted to determine whether the effect of treatment varies by subgroup.

Fisher's exact test will be used for TEAEs, discontinuations, and other categorical safety data for between-treatment group comparisons. Continuous vital signs, body weight, and other continuous safety variables, including laboratory variables, will be analyzed by an analysis of covariance (ANCOVA) with treatment and baseline value in the model. Shift tables for categorical safety analyses (for example, 'high' or 'low' laboratory results) will also be produced.

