### **6.2.3. Time-to-Event Analysis**

The primary analysis for time-to-event analysis will be the unstratified log-rank test. Treatment comparisons for time-to-event analysis may also be analyzed using a Cox proportional hazards model adjusted for baseline stratification variables (Section 6.1.4). The hazard ratio with 95% CIs will be reported. Kaplan-Meier curves may also be produced. Diagnostic tests for checking the validity of the proportional hazards assumption may be performed. If the assumption of proportional hazards is not justified, a statistical model capable of handling nonproportional hazards will be explored to assess treatment effect, such as a max-combo test (Lee 1996), restricted mean survival time model (Royston and Parmar 2013), and win ratio analysis (Pocock et al. 2012).

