## Description and Derivation of Other Secondary Outcomes

Measure	Variable	Derivation / Comment	Definition of Missing
Extubation	Time to definitive extubation	
Patients included: randomized patients who progress to OS 7 at any time on or prior to Day 27.
 
Start date: first date that patient progressed to OS 7 (this could be their baseline date if they progressed the first day on study, after baseline)
 
Event date: First date when patient is removed from invasive mechanical ventilation (i.e., OS 6 or less) for the last time on or prior to Day 28.
 
Censor date for patients who are OS 7 at their last observation or by Day 28: Date of last observation.
 
Censor date for patients who die after their Start Date: Date of what would have been their Day 28.
	Missing if NIAID-OS is missing and time to event of interest cannot be identified using remaining data.
Oxygen Saturation	Time to oxygen saturation $\geq 94\%$ on room air in days	
Patients included: randomized patients whose oxygen saturation (based on NEWS) is <math>< 94\%</math> at baseline.
 
Event Date: the first date that their oxygen saturation is <math>\geq 94\%</math> and their OS is <math>\leq 4</math>.
	Missing if NIAID-OS is missing or oxygen saturation status is missing and time to event of interest cannot be identified using remaining data.
Resting respiratory rate	Number of days of resting respiratory rate $< 24$ breaths per minute	
Total number of days when patients' resting respiratory rate <math>< 24</math> breaths per minute.
 
This will be based on values from NEWS.
	Missing if Patient's resting respiratory rate is missing for at least 1 day.

Abbreviations: ICU = intensive care unit; NIAID-OS = National Institute of Allergy and Infectious Diseases ordinal scale.

Table KHAA.6.7. Description of Other Secondary Analyses

Measure	Variable	Population	Analysis Method	Time Point	Analysis Type
NIAID-OS	Time to recovery by disease duration at baseline: < 7 days and ≥7 days	ITT	Log rank test using IETI	By Day 28	Secondary analysis
			Cox Proportional Hazards model using IETI	By Day 28	Supportive analysis
	Time to clinical deterioration	ITT	Log rank test	By Day 28	Secondary analysis
			Cox Proportional Hazards model	By Day 28	Supportive analysis
	Time to clinical improvement in one category	ITT	Log rank test using IETI	By Day 28	Secondary analysis
			Cox Proportional Hazards model using IETI	By Day 28	Supportive analysis

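### SAP 6.14 gives no treatment-by-subgroup interaction test for time to recovery or all-cause mortality, although Protocol 9.4.1 commits to interaction tests in its subgroup analyses

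*SAP*

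**What the plan says.** Protocol 9.4.1 sets the scope ("Subgroup analyses for the primary and selected key secondary outcomes will evaluate the treatment effect across the following subgroups") and then commits: "Interaction tests will be conducted to determine whether the effect of treatment varies by subgroup". No endpoint type is exempted.

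SAP 6.14 applies the severity, steroid and remdesivir subgroups broadly: "For primary and gated secondary endpoints, following subgroup analysis will be conducted". Time to recovery and all-cause mortality are both key secondaries, and Table KHAA.6.12 lists all subgroups for each.

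The SAP's methods differ by endpoint type:

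- Categorical and ordinal endpoints: a logistic or proportional-odds model with a treatment-by-subgroup term and an interaction p-value.
- Continuous endpoints: ANOVA with the same term and an F test for interaction.
- Time-to-event endpoints: "For the time-to-event endpoints, an unstratified log-rank test will be performed within each level of specified subgroups if sample sizes allow". The next sentence stays within levels: "Analysis of individual levels of subgroups will follow what is specified in Section 6.2.3, possibly with the use of the Firth correction".

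In Table KHAA.6.12 the method for recovery is "Log-rank test using IETI", and for mortality a log-rank test.

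**The concern.** A result within each level answers whether treatment works in that level. It does not answer whether the effect differs between levels, which is what a subgroup analysis is for and what the protocol sentence promises. If one level reaches p<0.05 and the other does not, the usual misreading is that the drug works only in the first.

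The question is a live one in this trial. Protocol 4.2 calls the impact of dexamethasone on baricitinib's efficacy unknown. Protocol 9.2 and SAP 5.2 power the study for a scenario with an effect of 0.040 in steroid users and 0.075 in non-users. Readers will therefore ask whether the recovery or mortality effect depends on steroid use, and for these two endpoints the plan supplies no test that answers them.

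**Working it through.** **Comparison of the texts.** The protocol sentence covers the primary and selected key secondary outcomes. It does not name recovery or mortality, but both are key secondaries and the SAP selects both, so the commitment reaches them. Of the seven key secondaries in SAP 6.11.2, five are analysed by logistic regression, proportional odds or ANOVA, and so have an interaction test. The two without one are the time-to-event endpoints.

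The Cox model in SAP 6.2.3 is optional. It adjusts for the stratification variables and has no treatment-by-subgroup term. Appendix 3 repeats time to recovery in four steroid-by-remdesivir cells, also without such a term. Protocol 9.4 requires changes to protocol methods to be described and justified in the SAP. The SAP revision history entry for 6.14 says only that the analyses were brought in line with current plans.

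**Size of the problem.** The documents give no figure to reproduce on this point: no power and no hazard ratio for recovery or mortality. The following is therefore an illustration.

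Inputs:
- Two-sided level 0.05 (SAP 6.1).
- Steroid split 60:40 (SAP 5.2, given there for illustration).
- Overall power for the endpoint: an assumption, 50% to 90%.
- The same true effect in both levels.

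Formulas (normal approximation, information proportional to level size):
- Overall mean z: θ = 1.960 + z(power).
- Mean z in a level with share f: θ√f.
- Power in that level: P(f) ≈ Φ(θ√f − 1.960).
- Probability that exactly one level is significant: Pa(1 − Pb) + Pb(1 − Pa).

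At 80% power, θ = 1.960 + 0.842 = 2.80. The level means are 2.80 × √0.6 = 2.17 and 2.80 × √0.4 = 1.77, with powers 0.583 and 0.425. Exactly one is significant with probability 0.583 × 0.575 + 0.425 × 0.417 = 0.51.

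| Assumed overall power | Level powers, 60:40 | Exactly one significant, 60:40 | Level powers, 80:20 | Exactly one significant, 80:20 |
|---|---|---|---|---|
| 50% | 0.330, 0.236 | 41% | 0.418, 0.142 | 44% |
| 80% | 0.583, 0.425 | 51% | 0.707, 0.240 | 61% |
| 90% | 0.709, 0.536 | 48% | 0.826, 0.305 | 63% |

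The 80:20 columns are a what-if. They are included because the SAP revision history says blinded data showed Population 2 to be much smaller than anticipated.

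With no effect at all, exactly one of two levels is significant in 2 × 0.05 × 0.95 = 9.5% of trials.

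**The interaction test.** Its statistic is (za/√f − zb/√(1−f)) / √(1/f + 1/(1−f)). Under a uniform effect each term in the numerator has mean θ, so the difference has mean 0 and the false-signal rate is 5%. One million simulated trials at 60:40 gave 4.9% with no effect and 5.0% with a uniform effect at 80% power.

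**Limit of that test.** At 60:40 the difference between levels has √(1/0.6 + 1/0.4) = 2.04 times the standard error of the overall effect. Take 80% overall power and a between-level difference as large as the overall effect. The mean z is then 2.80/2.04 = 1.37, and the power is about Φ(1.37 − 1.96) = 28%.

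**The case against.** Several points on the other side stand.

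- A reader might infer that the SAP offers nothing but log-rank p-values in each level. It does not say that. SAP 6.14 refers to 6.2.3, which allows an adjusted Cox model with hazard ratio and 95% confidence interval. The mention of a Firth correction, which has no meaning for a log-rank test, shows that a model is contemplated. Per-level hazard ratios are thus available as an option. Only the interaction test is absent.
- A reader might extend the point to the outcome "Time to recovery by disease duration at baseline: < 7 days and ≥7 days" as a further protocol breach. Table KHAA.6.7 already lists a Cox model for it. It is also an other-secondary outcome, outside the scope of the protocol sentence.
- A reader might take Protocol 4.2 to raise remdesivir too. It discusses dexamethasone only, and it addresses that through the two primary-endpoint populations. For the primary endpoint, SAP 6.14 does specify interaction tests for steroid and remdesivir use.
- These subgroup tests lie outside the multiplicity scheme in SAP 6.6, and no success criterion depends on them. Inference is limited to levels of sufficient size (for example more than 100 patients and at least one event per arm).
- Power for mortality may be well below 50%. By the same method at 60:40, the discordance rate falls to 29% at 30% power and 22% at 20%.

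None of this supplies the missing test. The size condition limits which levels are tested but does not compare them. A per-level hazard ratio helps the reader, but it is optional and leaves the comparison to the eye.

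**Conclusion.** The point holds. For time to recovery and all-cause mortality the SAP specifies level-by-level analysis without an interaction test. It specifies that test for every other key endpoint and gives no justification for the departure from Protocol 9.4.1.

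Under a uniform effect, discordant significance between two steroid levels would arise in about 41% to 51% of trials, against 5% false signals from an interaction test. This rests on the 60:40 split, assumed overall power of 50% to 90% and a normal approximation.

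Two stronger readings are not supported. One is that chance differences are bound to be reported as effect modification: the figures measure discordant p-values, not what readers conclude from them. The other is that the sponsor decided to drop the test: the SAP is silent, so the method is unspecified, and additional subgroup analyses remain allowed.

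The primary analysis is unaffected. The gap should still be closed, because it concerns mortality and a question the protocol itself leaves open.

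**What to change.** In SAP 6.14 and Table KHAA.6.12, add for time to recovery and all-cause mortality:

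- a Cox model with treatment, subgroup, treatment-by-subgroup interaction and the baseline stratification variables, using infinite event time imputation for recovery and a Firth correction where events are sparse;
- reporting of the interaction p-value together with each level's hazard ratio and 95% confidence interval;
- a statement that within-level log-rank p-values are descriptive.

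For baseline severity, the interaction test should use non-overlapping levels, since SAP 6.14 lists OS 5, OS 6 and the two combined. The same term can be added to the Cox model already listed for recovery by symptom duration. If the sponsor prefers not to test interaction for these endpoints, the SAP should say so and give the reason.

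The cost is one paragraph, two table rows and one model per subgroup factor and endpoint. There is a small downside. The model relies on proportional hazards, which SAP 6.2.3 already plans to check. Interaction tests also have low power, so the SAP should state that a non-significant interaction does not show a homogeneous effect.

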## 4. Study Objectives

### 4.1. Primary Objective

Objectives	Endpoints
Primary	
To evaluate the effect of baricitinib 4-mg once daily (QD) compared to placebo on disease progression in patients with COVID-19 infection	Proportion of patients who die or require non-invasive ventilation/high-flow oxygen or invasive mechanical ventilation (including extracorporeal membrane oxygenation [ECMO]) by Day 28 in the following populations: 
 
Population 1 - all randomized patients
 
Population 2 – patients who, at baseline, require oxygen supplementation (OS 5 and 6) and are not receiving dexamethasone or other systemic corticosteroids for the primary study condition.
 

The associated estimand for this objective is to measure the effect of treatment with baricitinib as assessed by proportion of patients who die or progress to requiring non-invasive ventilation/high-flow oxygen or invasive mechanical ventilation (including extracorporeal membrane oxygenation [ECMO]) by Day 28.

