### 6.4.3. Multiple Imputation

A multiple imputation method will be used to impute the missing NIAID-OS scores (Rubin, 1996). The multiply-imputed datasets will be used for the primary analyses of several endpoints involving the NIAID-OS scores. A total of 100 multiply-imputed datasets will be generated. For random number generation, the seed will be set 3012021. The multiple imputation will be performed in a stratified manner with the imputation performed separately for each of the following levels: (1) baricitinib patients with baseline NIAID-OS of 5 or 6 and baseline steroid use, (2) baricitinib patients with baseline NIAID-OS of 5 or 6 and no baseline steroid use, (3) other baricitinib patients, (4) comparator patients with baseline NIAID-OS of 5 or 6 and baseline steroid use, (5) comparator patients with baseline NIAID-OS of 5 or 6 and no baseline steroid use, and (6) other comparator patients. In all these strata, baseline steroid use is defined as in Section 6.1.4. These strata are slightly reduced from what might be expected in order to keep a sufficient number of patients in each stratum. Imputation will be performed using a Markov model where each transition to a future state is dependent on only the previous state. This approach is described in detail in [Appendix 2](#).

The intended estimand for the multiple imputation approach is based on the treatment policy strategy for handling intercurrent events (ICH E9R [ICH 2017]). In this strategy the value of the NIAID-OS score is the value of interest regardless of any intercurrent events that occurred. The NIAID-OS includes a state for death, and thus it is meaningful even for patients who have died.

If the between-imputation variance calculated while combining some analysis results of the multiply-imputed datasets is zero then that specific analysis will not be performed using multiple imputation. Instead, the observed data will be used to perform the same analysis.

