**Table KHAA.6.5. Description of Primary, Key Secondary, and Associated Supportive Analyses**

Measure	Variable	Population	Analysis Method	Time Point	Analysis Type
NIAID-OS	Proportion of patients who died or progressed to non-invasive ventilation or high-flow oxygen (OS $\geq$ 6)	ITT: Population 1 - all randomized patients	Logistic regression using MI	By Day 28	Primary analysis
		ITT: Population 2 – patients who, at baseline, require oxygen supplementation and are not receiving dexamethasone or other systemic corticosteroids for the primary study condition.	Logistic regression using MI	By Day 28	Primary analysis
		ITT	Logistic regression using LOCF	By Day 28	Supportive analysis
		ITT: Population 2	Logistic regression using LOCF	By Day 28	Supportive analysis
		Safety Population	Logistic regression using MI	By Day 28	Supportive Analysis
		ITT Population, excluding patients who die within 24 hours of baseline and have Do Not Resuscitate (DNR) or Do Not Intubate (DNI) orders	Logistic regression using MI	By Day 28	Sensitivity Analysis
		Ventilator free days (VFD)	ITT	ANOVA using MI	By Day 28
	Wilcoxon rank-sum test using LOCF			By Day 28	Supportive analysis
	Proportion of patients with 1-point improvement	ITT	Logistic regression using MI	Day 4, 7, 10, 14	Key secondary analysis
			Logistic regression using LOCF	Day 4, 7, 10, 14	Supportive analysis

Measure	Variable	Population	Analysis Method	Time Point	Analysis Type
	Time to recovery	ITT	Log-rank test using IETI	By Day 28	Key secondary analysis
			Cox proportional hazards model using IETI	By Day 28	Supportive analysis
			Max-combo test using IETI (if needed)	By Day 28	Supportive analysis
NIAID-OS	Overall improvement	ITT	Proportional odds model using MI	Day 4, 7, 10, 14	Key secondary analysis
			Proportional odds model using LOCF	Day 4, 7, 10, 14	Supportive analysis
	Duration of hospitalization	ITT	ANOVA using MI	By Day 28	Key secondary analysis
			Wilcoxon rank-sum test LOCF	By Day 28	Supportive analysis
	All-cause mortality	ITT	Log-rank test	By Day 28	Key secondary analysis
			Cox proportional hazards model	By Day 28	Supportive analysis
Safety					
			Log-rank test	By Day 28	Supportive analysis
			Cox proportional hazards model	By Day 28	Supportive analysis
Oxygen Saturation	Proportion of patients with change in oxygen saturation from <94% at baseline to $\geq$ 94% at the observed time point	ITT	Logistic regression using LOCF	Day 4, 7, 10, 14	Key secondary analysis

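### Table KHAA.6.12 plans only LOCF for the primary endpoint's steroid and remdesivir subgroups, so they have no counterpart to the primary MI analysis

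*SAP*

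**What the plan says.** SAP Table KHAA.6.5 makes "Logistic regression using MI" the primary analysis of the primary endpoint in Populations 1 and 2. It adds LOCF as a supportive analysis for the ITT population and for Population 2.

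SAP Section 6.14 puts baseline severity, baseline steroid use and baseline remdesivir use together in its first tier of subgroups, planned for the primary and gated secondary endpoints. Table KHAA.6.12 then assigns methods for the primary endpoint:

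- Severity within Population 1, and again within Population 2 ("ITT: Population 2 – baseline disease severity"), is listed once with MI and once with LOCF.
- "All subgroups other than baseline disease severity" has a single row, "Logistic regression using LOCF". Steroid use and remdesivir use fall here.

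Section 6.4.3 runs the imputation in six strata: each arm is split into OS 5 or 6 with steroids, OS 5 or 6 without steroids, and all others. It states: "In all these strata, baseline steroid use is defined as in Section 6.1.4".

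**The concern.** Steroid use is the effect modifier behind Amendment E. Protocol Section 9.2 bases the increase to about 1400 patients partly on the possibility that steroids weaken the treatment effect, and Protocol Section 4.2 calls the impact of dexamethasone on efficacy unknown. A reader will want the steroid subgroups and their interaction test next to the primary result.

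As planned, the two rest on different footings:

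- **Assumption.** LOCF carries a patient who leaves event-free as event-free to Day 28. The Markov-model MI in Appendix 2 lets later states be drawn under missing at random.
- **Patients.** Section 6.4.2 limits LOCF to patients with a baseline and a postbaseline value, so subgroup counts need not add up to the count in the primary analysis.
- **Intervals.** Section 6.14 uses Newcombe-Wilson intervals for LOCF and Wald intervals for MI.

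Exit may also carry information. Protocol Section 7.2 lists transfer to another hospital or unit, and need for another effective agent, among the grounds for leaving the study. Remaining event-free to Day 28 is a strong assumption for such patients.

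**Working it through.** **Methods side by side (primary endpoint)**

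| Analysis | MI planned | LOCF planned | Source |
|---|---|---|---|
| Population 1 / ITT | yes (primary) | yes (supportive) | Table KHAA.6.5 |
| Population 2 | yes (primary) | yes (supportive) | Table KHAA.6.5 |
| Severity, Populations 1 and 2 | yes | yes | Table KHAA.6.12 |
| Steroid Yes/No | no | yes | Table KHAA.6.12 |
| Remdesivir Yes/No | no | yes | Table KHAA.6.12 |

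The gap lies in the last two rows. The plan states no figure on this point, so what follows only illustrates possible size.

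**Event rates.** Protocol Section 9.2 (Amendment D) gives 25% on placebo and differences of 5 or 7.5 points, with N = 1000 and two-sided alpha 0.05. Its powers are reproduced with a pooled variance under the null and an unpooled variance under the alternative, 500 per arm:

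- 5 points: (0.05 − 1.96 × 0.02641) / 0.02636 = −0.067, power 47.3% (stated 47%).
- 7.5 points: (0.075 − 1.96 × 0.02587) / 0.02576 = 0.943, power 82.7% (stated 83%).

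The illustration uses 25% against 17.5%: difference 7.50 points, odds ratio 0.636.

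**Formula.** Let m be the share of an arm that leaves event-free and q the share of those who would later have an event. LOCF gives p − m·q. The placebo-minus-baricitinib difference changes by −(m_P·q_P − m_B·q_B).

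**Illustration A (assumption: q equals the arm's full event rate, so all dropouts leave before any event, and MI recovers p).** The LOCF rate is p(1 − m).

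| m placebo / baricitinib | LOCF difference (points) | LOCF odds ratio |
|---|---|---|
| 1% / 1% | 7.43 | 0.637 |
| 5% / 5% | 7.13 | 0.640 |
| 10% / 10% | 6.75 | 0.644 |
| 5% / 2% | 6.60 | 0.665 |
| 2% / 5% | 7.88 | 0.614 |
| 10% / 5% | 5.88 | 0.687 |
| 5% / 10% | 8.00 | 0.600 |

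**Illustration B (assumption: q = 15% in both arms, m = 6% on placebo and 3% on baricitinib).** Shift = 0.15 × (6 − 3) = 0.45 points.

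**Against sampling error.** Section 9.2's Amendment E illustration has 60% on steroids, leaving 0.40 × 1400 = 560 without, or 280 per arm. SE = √(0.25 × 0.75/280 + 0.175 × 0.825/280) = 3.4 points. The 0.45-point shift is 0.13 SE. The 10%/5% case shifts the difference by 7.50 − 5.88 = 1.62 points, about 0.47 SE.

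**Interaction.** On the risk-difference scale the interaction shifts by the no-steroid shift minus the steroid shift. If dropout patterns are alike in users and non-users, the two cancel.

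**The case against.** Several objections hold and limit the point.

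- **A like-for-like comparison exists.** Table KHAA.6.5 plans LOCF for ITT and Population 2, so the LOCF subgroups have LOCF neighbours. Only the comparison with the primary MI result is missing.
- **MI already covers steroid-free patients on oxygen.** It does so as Population 2's primary analysis and as the combined OS 5 and 6 level of Population 2's severity rows. What is not planned in Table KHAA.6.12 is an MI estimate for steroid users, for all non-users, or for the interaction.
- **Population 2 is not the no-steroid subgroup.** A reader might infer that nearly the same patients are analysed two incompatible ways. Population 2 comprises patients who "require oxygen supplementation (OS 5 and 6) and are not receiving dexamethasone or other systemic corticosteroids for the primary study condition". The no-steroid subgroup has no such restriction and also takes in OS 4, a randomisation stratum. The two could differ under any single method.
- **LOCF does not count every dropout as event-free.** Patients with no postbaseline value are left out, and Section 6.4 allows outcomes to be derived from other clinical data before imputation.
- **Appendix 3** repeats the primary analysis in four steroid-by-remdesivir cells if sample sizes allow. The method is not restated; it may be MI. These cells are exploratory and do not give the Yes/No estimates or the interaction test.
- **LOCF is the SAP's usual subgroup method.** Subgroups of ventilator-free days, 1-point improvement, overall improvement and duration of hospitalization also use it, although MI is their key secondary method.

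The last objection does not settle the matter. For the primary endpoint the SAP already departs from that convention for severity, in the same tier as steroid use. Sample size does not explain the difference: MI is planned by severity within Population 2, which the revision history calls much smaller than anticipated.

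**Conclusion.** The gap is real and narrow. For the primary endpoint, Table KHAA.6.12 plans no MI analysis of the steroid or remdesivir Yes/No subgroups, so their estimates and interactions cannot be read directly against the primary result. A reader might go further and infer that the primary conclusions are at risk; the documents do not support that. These subgroup analyses carry no alpha in the Section 6.6 testing scheme, and both primary tests use MI throughout.

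The size cannot be known from the documents, which give no missing-data rate; every dropout figure above is an assumption. If dropout is low and balanced between arms the effect is likely small. It grows if dropout differs by arm, and it reaches the interaction only in so far as that pattern also differs by steroid use. This is a low-cost consistency improvement to non-confirmatory analyses.

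**What to change.** In Table KHAA.6.12, add "Logistic regression using MI" rows for baseline steroid use and baseline remdesivir use on the primary endpoint, and keep the LOCF analysis as supportive, as is done for severity.

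The cost is two table rows and extra runs on imputed datasets that Section 6.4.3 already generates. Section 6.14 already sets out how MI subgroup percentages and intervals are reported. One limitation should be noted beside the new rows: the imputation strata do not separate remdesivir use at all, or steroid use outside OS 5 and 6. Imputed outcomes are drawn from models pooled over those factors, so the corresponding interactions may be slightly attenuated.
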